9.2.1. Serious Adverse Events

An SAE is any AE from this study that results in one of the following:

- death
- initial or prolonged inpatient hospitalization
- a life-threatening experience (that is, immediate risk of dying)
- persistent or significant disability/incapacity
- congenital anomaly/birth defect
- events considered significant by the investigator based upon appropriate medical judgment

Study site personnel must alert Lilly, or its designee, of any SAE within 24 hours of investigator awareness of the event via a sponsor-approved method. If alerts are issued via telephone, they are to be immediately followed with official notification on study-specific SAE forms. This 24-hour notification requirement refers to the initial SAE information and all follow-up SAE information.

Although all AEs are recorded in the eCRF after signing informed consent, SAE reporting begins after the subject has signed informed consent and has received investigational product. However, if an SAE occurs after signing informed consent, but prior to receiving investigational product, AND is considered reasonably possibly related to a study procedure then it MUST be reported.

Investigators are not obligated to actively seek AEs or SAEs in subjects once they have discontinued from and/or completed the study (the subject summary eCRF has been completed). However, if the investigator learns of any SAE, including a death, at any time after a subject has been discharged from the study, and he/she considers the event reasonably possibly related to the study treatment or study participation, the investigator must promptly notify Lilly.

Pregnancy (maternal or paternal exposure to investigational product) does not meet the definition of an AE. However, to fulfill regulatory requirements, any pregnancy should be reported following the SAE process to collect data on the outcome for both mother and fetus.

9.2.1.1. Suspected Unexpected Serious Adverse Reactions

Suspected unexpected serious adverse reactions (SUSARs) are serious events that are not listed in the IB and that the investigator identifies as related to investigational product or procedure. United States 21 Code of Federal Regulations 312.32 and European Union Clinical Trial Directive 2001/20/EC and the associated detailed guidances or national regulatory

requirements in participating countries require the reporting of SUSARs. Lilly has procedures that will be followed for the recording and expedited reporting of SUSARs that are consistent with global regulations and the associated detailed guidances.

9.2.2. Complaint Handling

Lilly will forward product complaints on LY3314814 to AstraZeneca in order to ensure the safety of study participants, monitor quality, and to facilitate process and product improvements.

Subjects should be instructed to contact the investigator as soon as possible if he or she has a complaint or problem with the investigational product so that the situation can be assessed.

Complaints related to concomitant drugs are reported directly to the manufacturers of those drugs in accordance with the package insert.

The investigator or his/her designee is responsible for handling the following aspects of the product complaint process in accordance with the instructions provided for this study:

- recording a complete description of the product complaint reported and any associated AEs
- communicating the product complaint within 24 hours to Lilly or its designee

If the investigator is asked to return the product for investigation, he/she will return a copy of the product complaint correspondence with the product.

9.3. Treatment of Overdose

For the purposes of this study, an overdose of LY3314814 or rosuvastatin is considered any dose higher than the assigned dose. There is no specific antidote for LY3314814. There is no specific treatment in the event of rosuvastatin overdose. In the event of an overdose, the subject should receive appropriate supportive care and any AEs should be documented.

Refer to the LY3314814 IB and Crestor Product Label for more information.

9.4. Safety

9.4.1. Laboratory Tests

For each subject, clinical laboratory tests detailed in [Appendix 2](#) should be conducted according to the Schedule of Activities (Section 2).

9.4.2. Vital Signs

For each subject, vital signs measurements should be conducted according to the Schedule of Activities (Section 2).

Supine blood pressure and pulse rate should be measured after at least 5 minutes supine rest. Following the respective supine vital signs measurement, subjects will sit for approximately 1 minute and then standing blood pressure and pulse rate should be taken at 2 minutes, but no longer than 3 minutes, and at 5 minutes in a standing position.

If the subject feels unable to stand, supine and seated vital signs will be recorded.

Unscheduled orthostatic vital signs should be assessed, if possible, during any AE of dizziness or posture-induced symptoms. Additional vital signs may be measured during each study period if warranted and agreed upon between the sponsor and investigator.

Body temperature will be measured as specified in the Schedule of Activities (Section 2) and as clinically indicated.

9.4.3. Electrocardiograms

For each subject, a single 12-lead digital ECG will be collected according to the Schedule of Activities (Section 2). Electrocardiograms must be recorded before collecting any blood for safety or PK tests and before vital signs measurements. Subjects must be supine for at least 5 minutes before ECG collection and remain supine but awake during ECG collection.

Electrocardiograms may be obtained at additional times, when deemed clinically necessary. All ECGs recorded should be stored at the investigational site.

Electrocardiograms will be interpreted by a qualified investigator (or designee) at the site as soon after the time of ECG collection as possible, and ideally while the subject is still present, to determine whether the subject meets entry criteria at the relevant visit(s) and for immediate subject management, should any clinically relevant findings be identified.

If a clinically significant finding is identified (including, but not limited to, changes in QT/QTc interval from baseline) after enrollment, the investigator will determine if the subject can continue in the study. The investigator, or qualified designee, is responsible for determining if any change in subject management is needed, and must document his/her review of the ECG printed at the time of collection. Any new clinically relevant finding should be reported to Lilly, or its designee, as an AE via eCRF.

9.4.4. Physical Examination

Physical examinations and routine medical assessments will be conducted as specified in the Schedule of Activities (Section 2) and as clinically indicated.

9.4.5. Body Weight

Body weight will be recorded as specified in the Schedule of Activities (Section 2) and as clinically indicated.

9.4.6. Columbia-Suicide Severity Rating Scale

The C-SSRS captures the occurrence, severity, and frequency of suicide-related thoughts and behaviors during the assessment period (Posner et al. 2007a, 2007b). The scale includes suggested questions to solicit the type of information needed to determine if a suicide-related thought or behavior occurred. Certified site personnel will administer the C-SSRS assessment and a corresponding self-harm supplement form as specified in the Schedule of Activities (Section 2) and as clinically indicated. If a self-harm event is reported, investigators will also complete the “self-harm follow-up” form. If the subject does not attend the discontinuation visit,

the C-SSRS and “self-harm supplement” form should still be completed if the site has become aware of a suicide-related thought or behavior by other communications. If a self-harm or suicidal-related event is considered serious by the investigator, it must be reported as an SAE via the procedures indicated in Section 9.2.1. If a clinically significant finding is identified, the investigator will determine if the subject can continue in the study. The investigator or qualified designee is responsible for determining if any change in subject management is needed.

9.4.7. Safety Monitoring

The Lilly CP or CRP/scientist will monitor safety data throughout the course of the study.

Lilly will review SAEs within time frames mandated by company procedures. The Lilly CP or CRP will consult with the functionally independent Global Patient Safety therapeutic area physician or clinical research scientist when appropriate, and periodically review:

- trends in safety data
- laboratory analytes
- AEs

If a study subject experiences elevated ALT ≥ 3 times ULN, ALP ≥ 2 times ULN, or elevated TBL ≥ 2 times ULN, liver testing ([Appendix 4](#)) should be repeated within 3 to 5 days to confirm abnormality. If the abnormality persists or worsens, further clinical and laboratory monitoring should be initiated by the investigator in consultation with the Lilly-designated medical monitor.

In the event a subject experiences a suspected drug-induced rash, the following procedures should be followed:

- The subject should be referred to a dermatologist for an expert opinion.
- A photograph of the rash should be taken.
- A blood sample should be drawn for PK analysis, if >12 hours since the last PK sample.

If treatment is discontinued due to a suspected drug-induced rash, the Lilly-designated medical monitor should be notified as soon as possible, even if the rash did not meet the definition of an SAE.

9.5. Pharmacokinetics

At the visits and times specified in the Schedule of Activities (Section 2), venous blood samples of approximately 2 mL each will be collected to determine the plasma rosvastatin concentrations and samples of approximately 2 mL each will be collected to determine the plasma LY3314814 concentrations. A maximum of 3 samples may be collected at additional time points during the study if warranted and agreed upon between both the investigator and sponsor. Instructions for the collection and handling of blood samples will be provided by the sponsor. The actual date and 24-hour clock time of each sampling will be recorded.

9.5.1. Bioanalysis

Samples will be analyzed at a laboratory approved by the sponsor and stored at a facility designated by the sponsor.

Plasma rosuvastatin and LY3314814 concentrations will be assayed using validated liquid chromatography with tandem mass spectrometry methods.

Bioanalytical samples collected to measure investigational product concentrations will be retained for a maximum of 2 years following last subject visit for the study. During this time, samples remaining after the bioanalyses may be used for exploratory analyses such as metabolism and/or protein binding work.

9.6. Pharmacodynamics

Not applicable for this study.

9.7. Genetics

A blood sample will be collected for pharmacogenetic analysis as specified in the Schedule of Activities (Section 2), where local regulations allow.

Samples will not be used to conduct unspecified disease or population genetic research either now or in the future. Samples will be used to investigate variable response to LY3314814 or rosuvastatin, and particularly to investigate the effect of polymorphisms on the disposition of LY3314814 and rosuvastatin. Samples may be used to investigate genetic variants thought to play a role in AD. Assessment of variable response may include evaluation of AEs.

All samples will be coded with the subject number. These samples and any data generated can be linked back to the subject only by the investigative site personnel.

Samples will be retained for a maximum of 15 years after the last subject visit, or for a shorter period if local regulations and/or ethical review boards (ERBs) impose shorter time limits, for the study at a facility selected by Lilly or its designee. This retention period enables use of new technologies, response to regulatory questions, and investigation of variable response that may not be observed until later in the development of LY3314814 or after LY3314814 is commercially available.

Molecular technologies are expected to improve during the 15-year storage period and therefore cannot be specifically named. However, existing approaches include whole genome or exome sequencing, genome wide association studies, multiplex assays, and candidate gene studies. Regardless of technology utilized, data generated will be used only for the specific research scope described in this section.

9.8. Biomarkers

Biomarker research is performed to address questions of relevance to drug disposition, target engagement, pharmacodynamics, mechanism of action, variability of patient response (including safety), and clinical outcome. Sample collection is incorporated into clinical studies to enable

examination of these questions through measurement of biomolecules including DNA, RNA, proteins, lipids, and other cellular elements.

Serum and plasma samples for non-pharmacogenetic biomarker research will be collected at the times specified in the Schedule of Activities (Section 2) where local regulations allow.

Samples will be used for research on the drug target, disease process, variable response to LY3314814 or rosuvastatin, pathways associated with neurological disease, mechanism of action of LY3314814 or rosuvastatin, identification of LY3314814 metabolites, and/or research method, or for validating diagnostic tools or assay(s) related to neurological disease.

All samples will be coded with the subject number. These samples and any data generated can be linked back to the subject only by the investigative site personnel.

Samples will be retained for a maximum of 15 years after the last subject visit, or for a shorter period if local regulations and/or ERBs impose shorter time limits, at a facility selected by Lilly or its designee. This retention period enables use of new technologies, response to regulatory questions, and investigation of variable response that may not be observed until later in the development of LY3314814 or after LY3314814 is commercially available.

9.9. Health Economics

This section is not applicable for this study.

10. Statistical Considerations and Data Analysis

10.1. Sample Size Determination

Up to 42 subjects may be enrolled in order that 24 subjects complete the study.

For rosuvastatin AUC, the intrasubject variability (coefficient of variation) was estimated to be 25.5% by assuming intrasubject variability comprised half of the total variability of 51% (CDER 2003); Martin et al. (2016) estimated the intrasubject variability of rosuvastatin AUC to be 21%. A sample size of 24 subjects will provide 92.3% probability that the estimated AUC geometric mean ratio will be within 0.15 of the upper and lower bounds of the 90% confidence interval (CI) in the log scale, which corresponds to approximately 0.162 in the natural scale.

While this study is not powered for the C_{max} geometric mean ratio to be within 0.15 of the upper and lower bounds of the 90% CI in the log scale, the C_{max} power calculations are described here to give the expected results context. For rosuvastatin C_{max} , the intrasubject variability was estimated to be 35.9% by assuming intrasubject variability comprised half of the total variability of 71.8% (CDER 2003); Martin et al. (2016) estimated the C_{max} intrasubject variability of rosuvastatin to be 34%. A sample size of 24 subjects will provide 19.6% probability that the estimated C_{max} geometric mean ratio will be within 0.15 of the upper and lower bounds of the 90% CI in the log scale.

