5.5. Justification for Dose

A dose of 50 mg LY3314814 administered orally QD was selected based on current clinical study data. LY3314814 doses up to 750 mg (highest planned dose) were well tolerated in the single ascending dose study. Multiple LY3314814 doses up to 150 mg QD for 12 days were also well tolerated. The 50-mg dose of LY3314814 selected for this study is the highest dose that is being used in the ongoing Phase 3 studies, and is the highest planned dose in Phase 3 studies.

Rosuvastatin is commonly administered to adults at an oral dose of 5 to 40 mg QD, with the majority of the clinical drug-drug interaction or pharmacogenetic studies conducted using a 10- or 20-mg dose (Crestor Prescribing Information; Lee et al. 2015). Rosuvastatin administered orally at a dose of 20 mg is suggested as a good clinical probe for both hepatic and intestinal BCRP function (Lee et al. 2015). Coadministration of rosuvastatin with LY3314814 may increase rosuvastatin exposure. Using calculations similar to those described by Elsby and colleagues (2016) and the assumption that LY3314814 will only inhibit BCRP in the intestine, it is estimated that LY3314814 may increase rosuvastatin exposures by approximately 70%. The 20-mg rosuvastatin dose selected for this study should provide adequate plasma rosuvastatin concentrations to address the study objectives with minimal risk for AEs.

6. Study Population

Eligibility of subjects for study enrollment will be based on the results of screening medical history, physical examination, vital signs, clinical laboratory tests, C-SSRS, and safety ECG.

The nature of any conditions present at the time of the physical examination and any preexisting conditions will be documented.

Screening may occur up to 45 days prior to enrollment. Subjects who are not enrolled within 45 days of screening may be subjected to an additional medical assessment and/or clinical measurements to confirm their eligibility. Subjects who meet all other screening eligibility criteria will return for a second screening visit, at least 21 days prior to enrollment, when samples will be collected for genotype analysis. Genotyping only needs to be conducted once, regardless of the 45-day screening window and any repeated assessments to confirm eligibility.

Prospective approval of protocol deviations to recruitment and enrollment criteria, also known as protocol waivers or exemptions, are not permitted.

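### Does the precision claim behind n = 24 rest on a wrong variance split and a wrong natural-scale figure?

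*Protocol*

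**What the plan says.** Protocol section 10.1 states that for rosuvastatin AUC "the intrasubject variability (coefficient of variation) was estimated to be 25.5" percent, obtained "by assuming intrasubject variability comprised half of the total variability of 51" percent. Beside this it cites a published study that "estimated the intrasubject variability of rosuvastatin AUC to be 21" percent. The precision statement follows: "A sample size of 24 subjects will provide 92.3% probability that the estimated AUC geometric mean ratio will be within 0.15". Here 0.15 is the distance from the estimate to either limit of the 90% interval for the log ratio. In other words, the half-width of that interval should be at most 0.15. A gloss for the untransformed ratio is then added: "which corresponds to approximately 0.162 in the natural scale".

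For Cmax the same rule is used, "by assuming intrasubject variability comprised half of the total variability of 71.8" percent, giving a CV of 35.9% against a published 34%. The stated probability is 19.6%, and the protocol says plainly that the study is not powered for Cmax.

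SAP section 7 carries the same figures. Elsewhere, in the dose justification (Protocol section 5.5), "it is estimated that LY3314814 may increase rosuvastatin exposures by approximately 70" percent, on the assumption that only intestinal BCRP is inhibited.

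**The concern.** This paragraph is the justification for 24 completers, so an error in it would matter.

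The first doubt is about the word half. The planned analysis has subject as a random effect, and in that model the between- and within-subject parts add as variances. Half of the variability would ordinarily mean half of the variance. Halving the CV gives the within-subject part roughly a quarter of it. If half of the variance was meant, the within-subject CV is 35.0%, and 24 completers would meet the 0.15 target about one time in four instead of nine times in ten.

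The second doubt is about 0.162. A distance on the log scale is a multiplicative factor, so it has no single absolute equivalent. A reader who puts plus or minus 0.162 around a ratio of 1.70, the increase foreseen in the dose justification, would expect an interval of about 1.54 to 1.86, which is too narrow on both sides.

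**Working it through.** **Inputs.** From Protocol section 10.1: n = 24; CV 25.5% (AUC) and 35.9% (Cmax); total CV 51% and 71.8%; published within-subject CV 21% and 34%; 90% CI; log half-width target 0.15. From Protocol section 5.5: a ratio of about 1.70. The design is paired, with each subject as own control, so df = 23.

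**Formulas.**
- σ_w = √ln(1 + CV²)
- Half-width at the planning SD: h = t(0.95, 23) × σ_w × √(2/24) = 1.714 × σ_w × 0.2887
- P(half-width ≤ 0.15) = P(χ²₂₃ ≤ 23 × (0.15/h)²)
- The conditional version restricts this to intervals that cover the true ratio.

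**Reproducing the plan, AUC.** σ_w = √ln(1 + 0.255²) = 0.2510; h = 0.1242; 23 × (0.15/0.1242)² = 33.56; probability 92.8%. Conditional on coverage it is 92.3%, which is the stated figure.

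**Reproducing the plan, Cmax.** σ_w = 0.3482; h = 0.1723; 23 × (0.15/0.1723)² = 17.44; probability 21.3%. Conditional on coverage it is 19.5%, against 19.6% stated.

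**What halving the CV implies.** The within-subject share of the log-scale variance is 0.2510²/0.4808² = 0.0630/0.2312 = 27% for AUC, and 0.1212/0.4158 = 29% for Cmax.

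**If half of the variance had been meant.**
- AUC: σ_w = √(0.2312/2) = 0.340, CV 35.0%, h = 0.168, probability 26% (24% conditional).
- Cmax: σ_w = 0.456, CV 48.1%, probability about 1%.

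**Set against the published within-subject estimates.**

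| | Published CV | Planning CV (half of total CV) | CV if half of variance |
|---|---|---|---|
| AUC | 21% | 25.5% | 35.0% |
| Probability, n = 24 | 99.9% | 92.8% | 26% |
| Cmax | 34% | 35.9% | 48.1% |
| Probability, n = 24 | 32% | 21% | 1% |

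Probabilities in the table are unconditional. The planning CVs lie slightly above the published ones. The half-of-variance CVs are 35.0/21 = 1.67 and 48.1/34 = 1.41 times the published ones.

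**Natural scale.** exp(0.15) − 1 = 0.162 and 1 − exp(−0.15) = 0.139, so the limits lie at 0.861 and 1.162 times the estimated ratio.
- At a ratio of 1, the distances are 0.162 above and 0.139 below.
- At 1.70, they are 1.70 × 0.1618 = 0.275 above and 1.70 × 0.1393 = 0.237 below, so the limits are 1.46 and 1.98. The upper distance is 0.275/0.162 = 1.70 times the stated one; put the other way, 0.162 is 41% too small there.
- As a relative figure, the upper limit is 16.2% above the estimate at any ratio and the lower limit 13.9% below it.

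**The case for a change.** The best case for a change is that one sentence can be read to support either 92% or 26%, depending on what was halved. The variance reading is the natural one for a mixed model, and no reason is given for choosing a half. The same paragraph already holds a better basis in the published 21%. The natural-scale remark covers both limits, yet 0.162 is exact for only one of them even in relative terms. Clarifying both points would take two sentences.

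Some of this stands. The halving is a rule of thumb without a stated rationale. Half of the total CV would be clearer wording, and a factor of 0.861 to 1.162 would say exactly what the 0.15 means.

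The rest does not hold. The text names the coefficient of variation as its measure in the same sentence, and 25.5 is exactly half of 51 on that scale, as 35.9 is of 71.8. The stated probabilities follow from those inputs, so no calculation is wrong. The 26% depends on a reading the text does not give and a CV far above the published one. For 0.162, the sentence does not say the distance is absolute. Read as a relative bound it is exact above and slightly generous below.

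**Conclusion.** No change is needed. The assumption is disclosed on a named scale, and 92.3% and 19.6% reproduce from it to within about 0.1 point conditional on coverage (within 2 points unconditionally). For AUC the planning CV errs on the cautious side of the only direct within-subject estimate in the documents: 25.5% against 21%, or 92.8% against 99.9%.

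The one imprecise item is the natural-scale gloss. Taken as an absolute distance at a ratio of 1.70 it understates the upper side (0.162 against 0.275) and the lower side (0.162 against 0.237). It has no consequence, because the criterion is 0.15 on the log scale, which does not depend on the ratio, and nothing in the analysis or interpretation uses 0.162. The 1.70 itself comes from the dose justification and is not a planning value for sample size.

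Rewording would leave n = 24, the mixed model, the 90% interval and every conclusion as they are. The verdict assumes a paired analysis with 24 completers and a true within-subject CV for AUC near the range of 21% to 25.5% given in the protocol. If the true CV were near 35%, the interval would be wider (half-width about 0.168) but still valid.
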